## Data Analysis

Statistical analyses will begin with the collection and reporting of demographic information for all study participants. This information will provide context for the sample and allow for appropriate interpretation of study outcomes.

Pre- and post-intervention survey data will be analyzed using paired-sample t tests. This approach will compare participant scores from the surveys administered at the beginning of the study to scores from the same surveys administered at the conclusion of the study, allowing for assessment of within-subject changes over time.

In addition to survey measures, objective sleep tracker data will be analyzed using paired-sample t tests. This will allow for comparison of baseline sleep measures with post-intervention measures, providing an additional source of quantitative evidence regarding the impact of the intervention.

All statistical analyses will be conducted using appropriate statistical software, and significance will be set at  $p < .05$ .

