Study Protocol

Effects of Sleep hygiene Education on Sleep Health in Adults Ages 50 -80

[name]

Updated: 09/02/2024

NCT: 06129045

Approved by human subject protection review board committee on 09/02/2024

Experimental design: The two-year randomized control trial will begin in the fall (September 2023) and conclude before the end of the academic year (May 2025). The principal investigator and student researcher(s) will recruit participants through flyers and word of mouth. Flyers will be placed at senior centers, community centers, and medical centers in Rapid City, SD. Interested participants will email or call [name] to enroll in the study. [name] will meet with the participant to determine the eligibility status for the study. Due to the use of human subjects in this study, the research protocol will be approved by the University of South Dakota, Black Hills State University institutional review boards, and the National Institutes of Health before participant recruitment. Participant inclusion criteria will include participants ages 50-80, who own a smartphone with the capability of receiving text messages. Exclusion criteria: an untreated diagnosed sleep disorder such as insomnia or obstructive sleep apnea, and inability to wear any sleep tracking device on their wrist. During the initial visit, participants will read through and sign informed consent explaining the procedures and expectations of them during the study. The participants will then complete the following questionnaires related to the primary objectives of the study: the Ru-SATED questionnaire which includes the Sleep Diary (based on the Consensus Sleep Diary) and Epworth Sleepiness Scale, Pittsburgh Sleep Quality Index, and the Sleep Hygiene Index. Participants will also complete the Perceived Stress Scale, and the Numeric Pain Rating Scale as secondary outcomes. Initial data collection will consist of taking anthropometric measurements and vital signs, with the assistance of the student researcher. The anthropometric measurements will include the following: body weight, height, and body mass index (BMI). BMI will be calculated by the standard method (body weight [kg]/ height [m]2) from weight and height measurements. The vital signs assessed will be resting blood pressure, heart rate, and respiratory rate. Following anthropometric data collection and vital signs, the participants will be instructed on the use of the wearable sleep tracker and assisted with setting up and charging the device. Participants will be instructed to contact the PI with any questions throughout the study by email or phone.

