
A total of 120 participants will be recruited with 40 participants per group. The 40 participants per group are based on recently performed studies related to text messaging and sleep health. Participants will be randomly assigned to one of three groups. The three groups will consist of a control group in which no intervention will be performed, a one-time educational group that will watch a sleep hygiene video on behavior changes related to healthy sleep, and the third group will get the one-time educational video plus daily automated text messages reinforcing education learned in the video.

Following the initial meeting with the PI, all participants will wear the sleep tracker on their wrist for 2 weeks to collect preliminary data and then 4 additional weeks following their intervention for a total of 6 weeks. The sleep tracker will monitor the physiological markers of sleep provided by wearable technology on sleep efficiency, time in bed, time actually sleeping, sleep midpoint, and time spent at each stage of sleep. At the end of the 6-week study period, the PI and/or student researcher(s) will again meet with each participant. The participant will again complete the following questionnaires: Sleep diary, Epworth Sleepiness Scale, Pittsburgh Sleep Quality Index, Sleep Hygiene Index, Perceived Stress Scale, and Numeric Pain Rating Scale. Anthropometric data collection and vital signs will be reassessed. Pre/post measurements will be compared and data analyses will be conducted using a 2x2 mixed factorial repeated measures ANOVA test.

Assessing overall sleep health is relatively new and therefore there is no established gold standard, however the Ru-SATED questionnaire (Table 1) has been shown to be a reliable and valid measure of sleep health(26). We will use this in combination of objective data from the FitBit device to measure sleep health. Each sleep health domain will be dichotomized using the cut-off points in Table 1 with 0 = poor sleep health and 1 = good sleep health. The domains will be summed to create the composite sleep health score ranging from 0 - 6 with a higher score indicating better sleep health.

Table 1 Sleep Health Composite			
Sleep health domain	Source	Operational definition	Cut-off for good sleep health
Regularity	FitBit	Standard deviation of sleep midpoint, which is calculated as [sleep onset + (wake time – sleep onset/2)]	<60 min

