Satisfaction	Sleep Diary	The sleep diary includes an item to rate “restedness upon awakening” with 0 = “not at all”, 1 = “somewhat”, 2 = “moderately”, 3 = “quite a bit”, and 4 = “extremely”. Satisfaction will be operationalized as the average “restedness” score	Average of ≥ 3
Alertness	Epworth Sleepiness Scale	Epworth Sleepiness Scale which consists of 8-items of various activities (ie. sitting and reading, watching TV, etc) answered using a 4-point Likert Scale with 0 = “would never nod off” to 3 = “high chance of nodding off”	≤ 10
Timing	FitBit	Average sleep midpoint	2am-4am
Efficiency	FitBit	Average total minutes of sleep divided by time in bed multiplied by 100	>85%
Duration	FitBit	Average total minutes of sleep	6-8 hours

Table 1: Sleep Health Composite

[figure not shown]

Figure 1: Study design for Specific Aim 1.

Specific Aim 2: Assess the ability of daily automated text messaging in CDOA to serve as an effective augmentation for sleep hygiene education. Several research studies have shown that a one-time sleep hygiene education session have improved sleep health in younger adults and working individuals(4, 27). With the promising results of a one-time education on short term progress, we want to test if longer-term reminders outside the initial training would provide even more sustainable results. The expansion of smartphone technology opens up an opportunity to reinforce the initial education with continual reminders of good sleep habits. A recent survey demonstrated that 86% of Americans over 50 utilize text messaging(28). In addition, one study showed text messaging significantly improved exercise rates in older adults(25). For this reason, we want to explore using automated text messaging for sleep hygiene education. *We hypothesize that automated text messaging will enhance the treatment effect of a one-time educational session on sleep health in CDOA.*

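### The SAP's Data Analysis section plans only pre/post paired t tests, so it contains no comparison of the randomised arms and cannot test the Aim 2 hypothesis

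*SAP*

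**What the plan says.** - **Design (Protocol, Experimental design).** 120 participants are randomised, 40 per group: "The three groups will consist of a control group in which no intervention will be performed", a group shown a sleep hygiene video once, and a group given the video plus daily text messages.
- **Hypothesis (Protocol, Specific Aim 2).** "We hypothesize that automated text messaging will enhance the treatment effect of a one-time educational session on sleep health in CDOA".
- **Protocol analysis (Experimental design).** Pre and post measurements are to be compared, and "data analyses will be conducted using a 2x2 mixed factorial repeated measures ANOVA test".
- **SAP, Data Analysis.** "Pre- and post-intervention survey data will be analyzed using paired-sample t tests". Likewise "objective sleep tracker data will be analyzed using paired-sample t tests", which the SAP describes as "providing an additional source of quantitative evidence regarding the impact of the intervention". Significance is set at p < .05. The section mentions no group, control, contrast, interaction or ANOVA, and does not say whether the paired tests are pooled over arms or run within each arm.

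**The concern.** Aim 2 concerns the difference between two randomised arms: video plus text against video. A paired t test, pooled or by arm, estimates a mean change over time. The SAP therefore answers a different question from the one the trial randomises people to answer, and the control arm has no inferential role.

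Two misreadings follow:

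- **Shared change read as intervention effect.** The protocol itself gives a possible route. Baseline questionnaires are completed at the first visit before the tracker is issued ("Following anthropometric data collection and vital signs, the participants will be instructed on the use of the wearable sleep tracker"). The final ones follow six weeks of wear in every arm, control included ("all participants will wear the sleep tracker on their wrist for 2 weeks to collect preliminary data and then 4 additional weeks"). Any effect of self-monitoring, repeat testing or regression to the mean would appear as pre/post change. For tracker outcomes the two-week baseline is itself recorded with the tracker on, so this particular route is weaker there.
- **Comparing significance across arms.** If the tests are run by arm, a significant change with texts and a non-significant one without may be taken as support for Aim 2. It is not a test of the difference.

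**Working it through.** **1. The two documents side by side**

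| | Protocol | SAP, Data Analysis |
|---|---|---|
| Test | Mixed factorial ANOVA | Paired t tests |
| Between-arm factor | Yes, with two levels | None |
| Fits 3 arms x 2 times? | Not as labelled (2x2) | Arms not mentioned |
| Gives video+text minus video? | Only if the two levels are those two arms, which is not stated | No |

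The arm sizes agree (3 x 40 = 120). The documents give no effect size, SD, correlation or power, so there is no planned figure to reproduce. A single 2x2 model must either omit one arm (40 of 120) or merge two. Merging the two education arms removes the Aim 2 contrast.

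**2. How often paired tests reject when the intervention does nothing**

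Assumed, because the documents give neither: a common drift d in SD units of the outcome, and a pre/post correlation r. The standardised change is dz = d / √(2(1−r)), the noncentrality is dz·√n, and the test is two-sided at 0.05. For example, r = 0.5 gives √(2 × 0.5) = 1, so d = 0.2 gives dz = 0.2. With n = 40 the noncentrality is 0.2 × 6.32 = 1.26 and the rejection probability is 0.235.

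| Test | d = 0 | 0.2 | 0.3 | 0.4 |
|---|---|---|---|---|
| One arm, n = 40, r = 0.3 | 0.050 | 0.181 | 0.346 | 0.550 |
| One arm, n = 40, r = 0.5 | 0.050 | 0.235 | 0.457 | 0.694 |
| One arm, n = 40, r = 0.7 | 0.050 | 0.357 | 0.666 | 0.890 |
| Pooled, n = 120, r = 0.5 | 0.050 | 0.584 | 0.903 | 0.991 |

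In 20,000 simulated trials (3 x 40, r = 0.5, d from 0 to 0.4, no arm effect), each ANCOVA contrast between arms rejected in 0.048 to 0.053. At least one of two unadjusted contrasts rejected in 0.089 to 0.093, and with Holm adjustment in 0.044 to 0.048.

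**3. Comparing p values across arms when texts add nothing**

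If both education arms change equally and each is significant with probability p, the text arm alone is significant with probability p(1−p). At r = 0.5 and n = 40:

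| Common change (SD) | 0 | 0.1 | 0.2 | 0.3 | 0.4 | 0.5 | 0.6 |
|---|---|---|---|---|---|---|---|
| p(1−p) | 0.048 | 0.09 | 0.18 | 0.248 | 0.212 | 0.114 | 0.04 |

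The maximum possible value is 0.25. A separate simulation that counted only improvements gave 0.241 at 0.3 SD, while the direct between-arm test of change rejected in about 5%.

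**4. What a valid comparison can detect**

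With 40 per arm, 80% power, two-sided 0.05 and no dropout, the normal approximation is (1.96 + 0.84) × √(2/40) = 0.63 SD of change (0.632 by the t distribution). ANCOVA multiplies this by √(1−r²), in SD of the outcome: 0.603, 0.547 and 0.451 at r = 0.3, 0.5 and 0.7. At r = 0.5 the SD of change equals the SD of the outcome, so 0.632 and 0.547 are directly comparable. At Holm's first step (0.025) the ANCOVA figure at r = 0.5 is 0.604. Power for a true 0.3 SD difference at r = 0.5 is 0.336 at 0.05 and 0.239 at 0.025.

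**The case against.** The strongest reply is that the protocol already plans a between-group analysis and the SAP never withdraws it. A 2x2 model of video against video plus text, by pre and post, would test Aim 2 through its group-by-time interaction. A second 2x2 of control against video would bring in the remaining arm. This is right as far as it goes: 2x2 models could serve. But the protocol names one such test and does not say which two arms it compares or that there is a series of them. The SAP, which should settle this, names a different test and does not mention the ANOVA. The conflict therefore stands, and copying the 2x2 sentence into the SAP would not resolve it.

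Three smaller points have merit:

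- The illustration rests on assumed drift and correlation, and the documents do not say that wearing a tracker changes questionnaire scores. The 0.3 SD figure in step 3 is close to the worst case. The conclusion needs none of these numbers.
- Part of the SAP outside Data Analysis was not available, so the statement is confined to that section.
- ANCOVA and Holm are choices. A correctly specified 3x2 group-by-time model is equally valid and closer to the protocol.

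**Conclusion.** The concern holds and must be fixed before analysis. The SAP's Data Analysis section prescribes tests that do not estimate the Aim 2 effect, or any effect relative to control, and it conflicts with a protocol analysis that is itself mislabelled for three arms. This follows from the text alone.

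The size of the error depends on how much change the arms share, which the documents do not give. With no shared change and no intervention effect, the paired tests keep their 5% level. At an assumed 0.2 to 0.4 SD over r = 0.3 to 0.7, a single arm would be declared improved in 18% to 89% of trials in which the intervention does nothing. Reading Aim 2 from separate p values would favour texts wrongly in up to about a quarter of trials.

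**What to change.** In the SAP's Data Analysis section, replace both paired-t sentences with wording such as:

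> For each survey and tracker outcome, including the 0–6 sleep health composite, the post value will be analysed by ANCOVA on randomised arm (control, video, video+text) and the baseline value of the same outcome. Two contrasts, video minus control and video+text minus video, will be reported with estimates and 95% confidence intervals; their two p values will be Holm-adjusted at two-sided 0.05. Within-arm changes are descriptive.

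A 3x2 group-by-time model with the same contrasts and Holm rule is an acceptable alternative. ANCOVA is preferred for precision (0.55 against 0.63 SD detectable at r = 0.5). Correct the 2x2 sentence in the protocol to match the chosen model. The Holm rule covers the two contrasts within an outcome; multiplicity across outcomes is a separate matter.

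**Cost.** Wording in two places and a little analysis work, with no new data or participants. The valid comparison is less precise than a within-arm test, and power for a 0.3 SD difference is only 24% to 34% at r = 0.5, so modest effects may be inconclusive. Dropout worsens this: with an assumed 34 completers per arm, the detectable differences grow by √(40/34) = 1.085, to about 0.59 and 0.69 SD.

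### The available SAP text relies on paired pre/post t tests to show intervention impact in a three-arm randomized trial, with no between-arm test, and conflicts with the protocol's mixed ANOVA

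*SAP*

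**What the plan says.** **SAP, Data Analysis** (the only SAP text available here). Pre and post survey scores go to paired-sample t tests, and so do baseline and post-intervention tracker measures. The stated target is within-subject change. The tracker tests are described as "providing an additional source of quantitative evidence regarding the impact of the intervention". The section closes: "All statistical analyses will be conducted using appropriate statistical software, and significance will be set at" p < .05. It mentions no group or arm, primary outcome, multiplicity rule or composite score. It does not say whether the paired tests are run by arm or pooled.

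**Protocol, first Experimental design section.** There are 120 participants, 40 in each of three arms: "The three groups will consist of a control group in which no intervention will be performed", a video arm, and a video-plus-daily-texts arm. Pre/post data are to be analysed with a 2x2 mixed factorial ANOVA with repeated measures. Sleep health is scored from six dichotomized domains (Table 1): "The domains will be summed to create the composite sleep health score ranging from 0 - 6". Several instruments are introduced as "questionnaires related to the primary objectives of the study", among them the Pittsburgh Sleep Quality Index (PSQI) and the Sleep Hygiene Index. Two others rank lower: "Participants will also complete the Perceived Stress Scale, and the Numeric Pain Rating Scale as secondary outcomes". The tracker yields "sleep efficiency, time in bed, time actually sleeping, sleep midpoint, and time spent at each stage of sleep".

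**Protocol, Specific Aim 2.** The hypothesis is that "automated text messaging will enhance the treatment effect of a one-time educational session on sleep health in CDOA".

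**The concern.** Randomization with an untreated arm lets the trial distinguish what the education did from what would have happened anyway. Participants in all arms wear a tracker for six weeks, complete the same instruments twice and know they are in a sleep study. Repeat testing, self-monitoring and regression to the mean could therefore shift scores in every arm. A paired test counts such a shift as an effect. If the tests are pooled, the untreated participants themselves contribute to the apparent impact of an intervention they did not receive.

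Aim 2 is a contrast between two arms, and no within-arm test answers it. A significant change in the text arm beside a non-significant one in the video arm is not a test of the difference between them.

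The protocol's ANOVA could supply the comparison, but the SAP does not mention it. A reader holding both documents cannot tell which analysis decides the trial.

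A smaller issue follows. With many measures each tested at .05 and none designated primary, any one significant result could be put forward as the finding.

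**Working it through.** **Plan's own figures.** 3 × 40 = 120 agrees with the stated total. The 40 per group cannot be rederived: the protocol cites earlier studies but gives no effect size, SD, power or dropout. The only other design figure is p < .05.

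**1. Change common to all arms.** Suppose every arm changes by the same amount, d in units of the SD of change, so the intervention effect is zero. The documents give no value for d; 0.2, 0.3 and 0.5 are assumptions. The paired t statistic is noncentral t with n − 1 degrees of freedom and noncentrality d√n. Taking the test as two-sided at .05, the critical value is 2.023 for n = 40 and 1.980 for n = 120.

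| Assumed d | d√40 | P(significant), one education arm | d√120 | P(significant), pooled |
|---|---|---|---|---|
| 0.2 | 1.265 | 23.5% | 2.191 | 58.4% |
| 0.3 | 1.897 | 45.7% | 3.286 | 90.3% |
| 0.5 | 3.162 | 86.9% | 5.477 | nearly 100% |

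In each row a valid between-arm test at .05 would reject 5% of the time. These figures are for a single outcome, so a multiplicity correction would not cure the problem.

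**2. Many measures at .05 (secondary).** The SAP lists no variables. Assume one score for each of the six instruments repeated at the end of study, the four named tracker measures, and 1 to 4 sleep stages: 6 + 4 + 1 = 11 up to 6 + 4 + 4 = 14. Now assume no change in any arm, and tests pooled over arms.

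- Independent: 1 − 0.95^11 = 43.1%; 1 − 0.95^14 = 51.2%.
- Common correlation of 0.3 to 0.5 between change scores (simulated paired t tests, n = 120): about 30% (11 measures, 0.5) to 44% (14 measures, 0.3).
- Common correlation of 0.8: about 18% to 20%.

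Independence is only an upper guide, because Table 1 computes efficiency from sleep time and time in bed. The documents give no correlations.

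**3. What a between-arm test can detect.** For two arms of 40, 80% power and no dropout, the noncentral t calculation gives a detectable difference of 0.634 SD at two-sided .05 and 0.701 SD at .025. Multiply by √(1 − r²) for ANCOVA, or by √(2(1 − r)) for group-by-time (change scores), where r is the assumed pre/post correlation:

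| r | ANCOVA, .05 to .025 | Group-by-time, .05 to .025 |
|---|---|---|
| 0.3 | 0.61 to 0.67 SD | 0.75 to 0.83 SD |
| 0.5 | 0.55 to 0.61 SD | 0.63 to 0.70 SD |
| 0.7 | 0.45 to 0.50 SD | 0.49 to 0.54 SD |

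These are approximate for a bounded 0-6 score.

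**The case against.** The strongest reply is that a group-based test is already documented. The protocol's mixed ANOVA has a group factor, it could be run as group-by-time for each pair of arms, and neither document says the SAP replaces it. The SAP also calls the tracker results additional evidence, not the sole basis. This stands to a degree: a reader might infer that the trial has no between-arm analysis planned anywhere, or that a 2x2 layout cannot serve three arms, and the documents support neither. What they do show is two different methods, no rule for which governs, and no statement of which arms the 2x2 covers.

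Second, the composite may already be covered. The protocol lists Ru-SATED among the questionnaires, and the SAP tests all survey data. That reading is possible, although four of the six domains in Table 1 come from the tracker. The fair statement is that the available SAP text does not name the composite, not that it is left untested.

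Third, a reader might take the composite to be the protocol's single primary outcome. No text says so. The PSQI and the Sleep Hygiene Index are also tied to the primary objectives, and neither enters the composite.

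Fourth, part of the SAP was not available, so statements about what is absent reach only the Data Analysis section.

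**Conclusion.** The point holds for the available SAP text. Followed as written, it would let pre/post change be reported as intervention impact without reference to the control arm, and it leaves Aim 2 without a test. It also disagrees with the protocol's method. The false-impact rate is about 23%, 46% or 87% in an education arm of 40, and about 58%, 90% or nearly 100% pooled, if all arms share a change of 0.2, 0.3 or 0.5 SD. The direction of this error is certain; its size depends on those assumed changes.

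The multiplicity point is real but secondary: roughly 18% to 51% for 11 to 14 assumed measures, depending on correlation. A reader might take the top of that range as the trial's actual error rate. The documents do not support that, since they give neither the list of tests nor their correlations. The protocol does partly rank outcomes, by calling stress and pain secondary, but the SAP section does not carry that ranking forward.

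**What to change.** In the SAP's Data Analysis section:

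- Make a between-arm test the deciding analysis for video vs control and for video plus texts vs video. State whether video plus texts vs control is also tested.
- Use either the group-by-time term of the protocol's mixed ANOVA, with the arms and times for each contrast spelled out, or an ANCOVA of post-intervention score adjusted for baseline. Make the protocol and SAP agree. Clarifying the existing ANOVA is the smaller edit; ANCOVA has the smaller detectable difference at each correlation shown.
- Keep within-arm paired tests as description only.
- State the primary outcome. The 0-6 composite is the natural candidate because the protocol defines it to measure sleep health, but the choice should address the PSQI and the Sleep Hygiene Index explicitly. Treat the remaining measures as secondary.
- State a multiplicity rule across the contrasts; Holm is one option.
- Date the change. The protocol has the trial ending by May 2025, so say whether outcome data had been examined and, if so, label the analysis post hoc.

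The cost is text changes in both documents and no new data. Moving from .05 to .025 (Holm's strictest step with two contrasts) raises the detectable difference by about 0.05 to 0.06 SD with ANCOVA and 0.05 to 0.08 SD with group-by-time, under the assumptions in the second table above.
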